## 2 INVESTIGATIONAL PLAN

### 2.1 OBJECTIVES

The primary objective of the study is to examine the effects of subject positioning on the ability of the CM-1500 parameters to detect minor blood loss.

Exploratory objectives of the study will include:

- Compare the performance of the CM-1500 monitoring during a whole blood donation with subjects positioned in either a fully supine position (180°) or in a reclined position (approx. 135°)
- Investigate any possible correlations between adverse events, subject demographics, changes in the individual parameters, and timing of when the events occurred.

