### 2.4 STUDY ENDPOINTS

The study endpoints include the change and percentage of change between measurements before and after blood draw in the Relative Index, individual parameters and standard physiological parameters. The change is defined as the value after draw minus the one before draw. The percentage of change is the change value divided by the value before draw. Other endpoints such as area under receiver operating characteristic (ROC) together with sensitivity and specificity at various thresholds are also derived for the Relative Index, individual parameters and each of standard physiological parameters in detecting in detecting minor blood loss (i.e., ~500mL).

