##### 3.1.3 PRINCIPLES OF OPERATION

The CM-1500 measures bioelectrical impedance (ohms), heart rate (BPM), ECG amplitude (mV), PPG amplitude, and skin temperature (°C or °F). As parameters change towards indications of fluid change/imbalance, the Relative Index, which acts as a combinational score of percent change values for all of the parameters, will compound these changes into a singular value to signify overall fluid changes/imbalances within the patient's body. When the monitoring session starts, every patient will start with a Relative Index of 100, signifying the combination of physiological parameters is near or at their original baseline values for all five monitored parameters. All parameters are continuously measured and tracked during a monitoring session. ECG and PPG amplitude values are only visible on the Advanced monitoring session display mode, as selected in the Setup screen.

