### 9.3 STATISTICAL ANALYSIS

#### 9.3.1 DESCRIPTIVE STATISTICS

Continuous data will be summarized in terms of the mean, standard deviation (SD), median, quartiles, minimum, maximum, and number of observations, unless otherwise specified. Categorical data will be summarized in terms of the number of subjects providing data at the relevant time point (n), frequency count, and percentage. Percentages will be calculated using n as the denominator.

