##### 1. Analysis of measurements taken before and after blood draw

Measurements including RI and individual physiological parameters taken before and after blood draw will be first summarized using descriptive statistics. For each parameter, the absolute and percent differences before and after draw will be calculated and summarized using summary statistics together with 95% confidence interval. The p-value will be calculated using paired t-test or Wilcoxon signed-rank test to compare with zero.

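### The primary analysis tests change against zero, but the primary objective is how position affects detection; Section 9 plans neither a detection estimate nor a comparison of positions.

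*Combined protocol and SAP*

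**What the plan says.** Section 2.1 sets the primary objective: to "examine the effects of subject positioning on the ability of the CM-1500 parameters to detect minor blood loss". An exploratory objective in the same section is to compare the monitor's performance between the supine and reclined positions.

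Section 9.3.4, the primary analysis, has two items. Under item 1, for the Relative Index (RI) and each parameter, "the absolute and percent differences before and after draw will be calculated and summarized using summary statistics together with 95% confidence interval", followed by "The p-value will be calculated using paired t-test or Wilcoxon signed-rank test to compare with zero". Item 2 defines a before-minus-after difference and names no test, model or comparison. Neither item mentions position.

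Section 2.4 adds: "Other endpoints such as area under receiver operating characteristic (ROC) together with sensitivity and specificity at various thresholds are also derived". Section 9 does not return to these endpoints. It gives no definition of a no-loss reading, no thresholds, no confidence interval and no split by position.

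Three other provisions bear on the point. Section 9.3.1 requires SDs: "Continuous data will be summarized in terms of the mean, standard deviation (SD), median, quartiles, minimum, maximum, and number of observations". Section 4.1 allows up to 60 subjects with at least 20 per position, and aims for an even split. Section 9.1 calls this a feasibility study without statistical hypotheses.

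**The concern.** Detection is a property of individual readings: does the change after roughly 500 mL stand out from the change that would occur with no loss? A test against zero asks whether the average change is nonzero. With enough subjects, a small p-value is compatible with readings that barely separate loss from no loss.

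The study could therefore report which parameters changed significantly and still leave its primary question unanswered. A reader might also take a smaller p-value in one position as better detection there, although the p-value depends on how many subjects were in that position.

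**Working it through.** **Inputs.** From the protocol: up to 60 subjects and at least 20 per position (Section 4.1), so 20/20, 30/30 and 40/20 are all possible; two-sided 5% tests (Section 9.3.4). The sample size rests on clinical judgment (Section 9.1), so there is no power figure to reproduce. The documents give no SD or effect size, and those used below are assumed.

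**Assumptions.** Changes after the draw are normal with mean m and SD s. No-loss changes are normal with mean zero and SD k·s, for k = 1, 0.5 and 0.25. Write d = m/s.

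**Formulas.**
- Paired t = d·√n, so the smallest d with p=0.05 is t(0.975, n−1)/√n.
- AUC = Φ(d/√(1+k²)).
- Sensitivity at 95% specificity = Φ(d − 1.645k).

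**Step 1: what p=0.05 implies for detection.**

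| n | d at p=0.05 | AUC, k=1 | AUC, k=0.5 | AUC, k=0.25 |
|---|---|---|---|---|
| 20 | 2.093/√20 = 0.468 | 0.63 | 0.66 | 0.68 |
| 30 | 2.045/√30 = 0.373 | 0.60 | 0.63 | 0.64 |
| 40 | 2.023/√40 = 0.320 | 0.59 | 0.61 | 0.62 |
| 60 | 2.001/√60 = 0.258 | 0.57 | 0.59 | 0.60 |

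At n=60 the AUC stays close to the chance value of 0.50 across the range of k. Sensitivity is far less stable. At n=60 it is Φ(0.258 − 1.645) = 8% for k=1, Φ(0.258 − 0.823) = 29% for k=0.5, and Φ(0.258 − 0.411) = 44% for k=0.25. No single sensitivity figure can be given from the documents.

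**Step 2: ranking positions by p-value with a 40/20 split.**
- Position A: mean 6, SD 10, n=40. d=0.60, t=0.60·√40=3.79, p=0.0005, AUC (k=1) = Φ(0.60/√2) = 0.66.
- Position B: mean 5, SD 7, n=20. d=0.714, t=0.714·√20=3.19, p=0.005, AUC (k=1) = Φ(0.714/√2) = 0.69.

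A has the smaller p-value and B the higher AUC. With any k common to both positions the AUC order is the same (k=0.25: 0.72 for A, 0.76 for B). The gap is small; the example shows that the p-value orders on the wrong quantity, not that a study of this size could separate the two.

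**Step 3: ranking with equal groups.** Take mean 3, SD 3 against mean 4, SD 8, with n=30 each. Raw mean change favours the second. The planned test gives t=1.0·√30=5.48 (p=0.000007) and t=0.5·√30=2.74 (p=0.010), favouring the first, as does the AUC at k=1 (0.76 against 0.64). With equal n and a common k, the paired t and the AUC always rank alike, because both increase with d.

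**Step 4: precision of a position comparison.** Using the Hanley-McNeil standard error and treating loss and no-loss values as independent, the 95% CI half-width for the difference in AUC is 0.23 to 0.14 at 20/20 and 0.19 to 0.12 at 30/30, for AUCs of 0.70 to 0.90. At 40/20 with AUC 0.80 it is 0.17. For the difference in d, taking SE² ≈ 1/n + d²/(2n) per position, the half-width at d=0.5 is 1.96·√[2(1/30 + 0.25/60)] = 0.54 at 30/30 and 0.66 at 20/20.

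**The case against.** A reader might infer that the plan ignores noise altogether. It does not: the paired t statistic is mean change over its SD, multiplied by √n, and Section 9.3.1 requires SDs. Mean change divided by SD can be recovered from planned output as t/√n, provided that output is produced by position, which Section 9.3.4 does not say.

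A reader might also infer that the plan would rank positions wrongly in general. Step 3 shows otherwise: with equal groups and comparable noise, the planned test ranks correctly. Misranking by p-value needs unequal groups, drift, or no-loss noise on a different scale. Unequal groups are permitted, although an even split is the aim.

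It is tempting as well to say that a significant result could go with sensitivity below 10%. That depends on the no-loss SD equalling the SD of change, which the documents do not establish. The SD of change also contains real differences in response, and Section 5.3 says the volume drawn varies by subject.

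Finally, detection measures are not absent, since Section 2.4 names them. The study is also declared hypothesis-generating, and no rule turns p<0.05 into a claim of detection.

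All of this stands, and it limits the consequence. It does not supply the missing piece: the named detection endpoints have no method in Section 9, and neither primary item compares positions.

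**Conclusion.** The point holds as a mismatch between objective and analysis. Followed as written, Section 9.3.4 yields no detection estimate and no comparison of positions, so the primary objective goes unanswered. A p-value against zero cannot stand in for it: at n=60 the threshold effect of 0.258 SD corresponds to an AUC of about 0.57 to 0.60, and with a 40/20 split the p-value can favour the position that detects worse. These figures assume normal changes, no-loss changes centred on zero, and a no-loss SD between one and one quarter of the SD of change.

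The documents do not support the stronger readings that the plan disregards variability, that it contains no detection endpoints, or that a wrong confirmatory conclusion would follow. In a feasibility study the cost is an unanswered question and a likely misreading. The plan should be changed, but the flaw does not invalidate the study.

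**What to change.** In Section 9.3.4, for RI and each parameter:

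1. Fix the expected direction of change in advance. Section 2.4 defines change as after minus before and item 2 uses the opposite sign, so choose one.
2. Make the primary summary the mean change divided by the SD of change, with a 95% CI for each position and for the difference between positions.
3. Report the Section 2.4 AUC, sensitivity and specificity by position, with CIs that allow for pairing within subject. Take the no-loss reference from windows in the pre-draw hold of at least ten minutes (Section 5.2). The traces exist: "All parameters are continuously measured and tracked during a monitoring session" (Section 3.1.3).
4. State that the p-value for change against zero is supportive and is not evidence of detection.

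The cost is a few sentences and some programming, with no new subjects, visits or procedures. There are real downsides. The hold is short, its readings are autocorrelated, and it does not capture drift over the whole draw, so the no-loss reference is approximate. Intervals will be wide (AUC-difference half-width about 0.12 to 0.23), and results may look less favourable than p-values.

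Scaling each subject's change by that subject's own SD during the hold, with a preset limit, is not recommended. With five independent normal one-minute means, and single-minute before and after values, a one-sided 2-SD limit is crossed without blood loss with probability P(t on 4 df > 2/√2) = 11.5%, against a nominal 2.3%.

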##### 2. Analysis of differences between measurement taken before and after blood draw.

The difference between measurements taken before and after blood draw will be calculated by value before donation minus value after draw for RI and each individual physiological parameter.

## CLINICAL PROTOCOL

SPONSOR: ZMS

PROTOCOL: ZMS-1500-Pa2023

## 10 DATA COLLECTION, RETENTION, AND MONITORING

### 10.1 DATA COLLECTION

The Investigator will prepare, maintain, and retain complete, current, accurate, organized, and legible Source Documents to record all observations and other pertinent data for each subject. In some instances, case report forms (CRFs) will serve as source documentation. The Investigator or designated study personnel will provide the Sponsor redacted standard procedure records with the subject ID number as applicable. Any required data not collected as standard of care for the blood draw procedure will be captured on study-specific case report forms.

Corrections of data on paper source documents will be made by crossing out the incorrect data and making the GCP-compliant correction. Each correction will be initialed and dated by the study personnel making the correction.

The Investigator is responsible for the information collected on subjects enrolled in the study. All data collected during the study must be reviewed and verified for completeness and accuracy by the Investigator. If any corrections are made after the Investigators signature, the Investigator will also initial and date the correction.

#### 10.1.1 SUBJECT CONFIDENTIALITY

In order to maintain subject confidentiality, records identifying the subject will be kept in a safe and secure location; access to these records will be on a limited basis. Only the subject identification number, gender, and age will identify study subjects on CRFs and other documentation submitted to the Sponsor. A limited number of Sponsor representatives may have access to identifiable information and will take reasonable precautions to maintain the confidentiality of the subject's identity.

### 10.2 DATA RETENTION

All study records will be stored in a safe and secure location. Records will be retained per applicable regulatory requirements, which include for a period of two (2) years after the latter of the following two days: the date which the investigation is terminated or completed, or the date that records are no longer required for purposes of supporting premarket approval applications or a notice of completion of a product development protocol. The Investigator site may transfer custody or records to the Sponsor with appropriate documentation recording the transfer.

### 10.3 MONITORING

#### 10.3.1 MONITORING PLAN

Monitoring visits will be conducted by representatives of the Sponsor or study site or both according to 21 CFR 812. (c) for non-significant risk device studies and ICH Guidelines. By signing this protocol, the Investigator grants permission to the Sponsor (or designee) and all appropriate regulatory authorities to conduct on-site or electronic monitoring or auditing or both of all appropriate study documentation.

## CLINICAL PROTOCOL

SPONSOR: ZMS

PROTOCOL: ZMS-1500-Pa2023

### 11 STUDY ADMINISTRATION

#### 11.1 AUDITS AND INSPECTIONS

External auditors and government inspectors may evaluate the study and must be allowed access to CRFs, source documents, and other study files. Audit reports will be confidential.

#### 11.2 PROTOCOL AND ICF AMENDMENTS

Sponsor approval is required for any protocol or ICF amendment. Protocol or ICF amendments will not be implemented without prior written IRB approval except as allowed per the IRB procedures/approval and as necessary to eliminate immediate safety hazards to subjects. A protocol amendment intended to eliminate an apparent immediate hazard to subjects may be implemented immediately, provided IRBs are notified within five (5) working days. The Informed Consent Form will be reviewed and updated as necessary at the time of the protocol amendment.

#### 11.3 PROTOCOL DEVIATIONS

A protocol deviation is defined as any accidental or unintentional changes to, or non-compliance with the IRB approved research protocol. Any deviation from the protocol must be documented and reported to the Sponsor within ten (10) working days and reported to the IRB as applicable to regulatory requirements. Protocol deviations that pose an immediate risk or significant hazard to subjects must be reported to the Sponsor within 24 hours and reported to the IRB no later than five (5) working days after the emergency occurred. In the instance an Investigator uses a device without obtaining informed consent; the Investigator shall report to the Sponsor and the IRB within five (5) working days as per 21 CFR 812.150 (1) (5).

### 12 ETHICAL AND OTHER REGULATORY CONSIDERATIONS

It is the responsibility of the Investigator that the study is conducted according to the Declaration of Helsinki, Protection of Human Volunteers (21 CFR 50), Institutional Review Board (21 CFR 56), and Responsibilities of Clinical Investigators (21 CFR 812 (e)).

#### 12.1 INSTITUTIONAL REVIEW BOARD (IRB) REVIEW

The Protocol, ICF, and any subject facing material (as required) will be reviewed and approved by the IRB prior to study initiation. The Sponsor will maintain responsibility for obtaining IRB approval and submitting all required study reports to the IRB. Amendments to the Protocol, ICF, or any subject facing material will not be implemented without prior written IRB approval unless to eliminate an apparent immediate hazard to subjects. All IRB approvals will be kept in the Trial Master File and Investigator Site File.

#### 12.2 WRITTEN INFORMED CONSENT

The Informed Consent Form (ICF) and Informed Consent process will include all elements required by applicable regulations. Informed consent will be obtained in accordance with the Declaration of Helsinki, ICH, Good Clinical Practice, and US Code of Federal Regulations for Protection of Human Subjects (21 CFR

## CLINICAL PROTOCOL

SPONSOR: ZMS

PROTOCOL: ZMS-1500-Pa2023

50.25 [a,b], 21 CFR 50.27, and 21 CFR Part 56, Subpart A), the Health Insurance Portability and Accountability Act (HIPAA) when applicable, and local regulations.

A properly executed, written informed consent will be obtained from all subjects prior to entering the subject into the trial, unless waived by the IRB. ICF information will be given in both verbal and written form. The subject must be given an ample amount of time to read the ICF. The subject must provide written consent by signing and dating the approved ICF. A signed copy of the ICF will be provided to the subject; originals will be maintained with the subject's study records.

[figure not shown]
Assents Forms will not be permitted as subjects must be over the age of 18 to meet the Inclusion/Exclusion criteria. Legally Authorized Representatives will not be permitted as subjects must have the ability to provide written consent to meet the Inclusion/Exclusion criteria.

## CLINICAL PROTOCOL

SPONSOR: ZMS

PROTOCOL: ZMS-1500-Pa2023

## CLINICAL PROTOCOL

SPONSOR: ZMS

PROTOCOL: ZMS-1500-Pa2023

### 14 ABBREVIATIONS AND DEFINITIONS OF TERMS

Table 6: Abbreviations and Definition of Terms

Abbreviation	Definition
AE	Adverse event
BPM	Beats per minute
BP	Blood pressure
C	Celsius
CFR	U.S. Code of Federal Regulations
CM-1500	Zynex Fluid Monitoring System, Model 1500
CRF	Case report form
ECG	Electrocardiogram
e.g.	Exempli Gratia (for example)
F	Fahrenheit
FDA	U.S. Food and Drug Administration
GCP	Good Clinical Practice
HIPAA	Health Insurance Portability and Accountability Act
HR	Heart rate
ICF	Informed Consent Form
ICH	International Council for Harmonization
IFU	Instructions for Use
IRB	Institutional Review Board
ISF	Investigator Site File
ISO	International Organization for Standardization
lb	Pound; unit of mass
ohms	Plural unit of electrical resistance
mL	Milliliter
mV	Millivolts
PHI	Protected Health Information
PI	Principal Investigator
PPG	Photoplethysmogram
SAE	Serious adverse event
UADE	Unanticipated Adverse Device Event
ZMS	Zynex Monitoring Solutions
